### 1.12.29 Clinical Laboratory

Blood samples for chemistry, hematology, lipids, pregnancy (if performed), complement (optional), genetic (optional), and drug PK (or related substances) shall be collected according to the schedule of assessment. During repeat or unscheduled visits, blood samples may also be collected to test the below analytes or because of technical issues with the samples.

Subjects do not need to be fasting at the time of blood collection: if not fasting, subjects may have had a light breakfast and have consumed water to avoid dehydration. Subjects’ fasting duration and number of hours elapsed since last study drug intake should be recorded. Blood samples should be handled according to a lab manual, labeled, then forwarded to either the central laboratory or the institution’s designated laboratory for testing.

**The PI must review all clinical laboratory reports** and document this review by dating and signing off on the report, marking any abnormal value as clinically significant (CS) or non-clinically significant (NCS). Clinically-significant abnormalities measured after start of treatment should be recorded as AE (see section [1.15.7.2](#) for details).

Sufficient blood should be drawn to perform the following tests:

- Lipids:
  - Total cholesterol,
  - HDL,
  - LDL,
  - Triglycerides.
- Biochemistry:
  - Sodium,
  - Potassium,
  - Chloride,
  - Bicarbonate,
  - BUN,
  - Creatinine (with computed eGFR CKD-EPI),
  - Calcium,
  - Total Protein,
  - Total Bilirubin,
  - Albumin,
  - Alkaline phosphatase (Alk Phos),
  - AST,
  - ALT.
- Hematology:
  - Hemoglobin (HGB),
  - Hematocrit (HCT),
  - Mean corpuscular volume (MCV),
  - Mean corpuscular hemoglobin (MCH),

- Platelets (PLT),
- Red blood cell (RBC) count,
- White blood cell (WBC) count,
- Neutrophils (absolute and percent),
- Lymphocytes (absolute and percent),
- Monocytes (absolute and percent),
- Eosinophils (absolute and percent),
- Basophils (absolute and percent).
- Glucose:
  - Random glucose (optional)

**Additional laboratory tests may be performed upon request by sponsor, or as clinically indicated by PI, but only after approval by sponsor (see section 1.17.12).**

### **1.12.30 Vitamin A and Pharmacokinetics (PK)**

Collection and processing of blood/plasma sample. The number of hours since the last study drug intake should be inquired and recorded. About 10 mL of blood will be collected in a K2-EDTA (purple top) tube. The tube will be pre-labeled and immediately covered with foil and placed in an ice bath if not immediately processed. The sample should be spun down for 10 minutes at 3,000-3,400 rpm or for the duration and at the rotational rate necessary to separate plasma, and plasma should then be transferred into 2 provided amber glass vials (one used as back-up in case of loss/damage), covered with foil, and immediately frozen.

At least 1 mL of plasma is required for proper testing. Because one (1) mL of plasma is necessary for proper testing of the plasma samples, the study team should ensure that at least one vial contains 1 mL of plasma.

Store frozen. Plasma samples should be stored frozen at approximately or below -20°C and preferably below -70°C for storage longer than 3 months, a duration which may be modified from time to time by sponsor.

Ship upon request. Periodically, the sponsor or representative will request the study team to ship available plasma samples to the bioanalytical lab, where a validated assay will determine the concentrations of various metabolites of ALK-001 and their corresponding non-deuterated vitamin A metabolites.

Lab manual to provide detailed instructions about the supplies, collection, handling and shipment.

### **1.12.31 Complement and Genotype**

Blood or saliva samples will be collected according to the manual of operations, to measure complement activity and/or the subject's genotype (optional). Please refer to section 1.7.2.10 for details. Samples may be stored long term and pooled for analysis.

### **1.12.32 Pregnancy Test at Screening, No Contraception Requirements**

Female subjects of childbearing potential will not be allowed to enroll in this study. For confirmation of absence of pregnancy before the start of treatment, PI may request a pregnancy test during the screening period.

There are no specific contraception requirements for subjects enrolled in the study. Nonetheless, if a male subject's female partner becomes pregnant during the treatment period, the pregnancy must be reported

to the sponsor within 24 hours of the site's knowledge of the pregnancy. Information on the pregnancy will be sought by the investigator until the end of the pregnancy (i.e. normal delivery, still birth, miscarriage).

### 1.12.33 Compliance (dietary and drug)

See section [1.10](#) for details.

### 1.12.34 Drug dispensing

See section [1.9.12.3](#)

### 1.12.35 Other Procedures

#### 1.12.35.1 Procedures/assessments prohibited outside of protocol

Subjects will be informed that they must not undergo any other ocular tests, exams or procedures, performed by any other optometrist or ophthalmologist who is not an investigator in the study, until the end of the study.

Except in case of a technical issue (eg: insufficient collected blood) or insufficient quality (eg: retinal imaging performed without following the manual of operation), or in the case of medical emergency or necessity which should be documented, investigator must not perform, allow, or request performance, of any procedure, ocular or blood, imaging, electrophysiological, psychophysical or any other test procedure or assessment that is not scheduled on the events table of section [1.2](#), unless an approvable exception is provided by sponsor, so as to preserve the integrity or quality of the data.

## 1.13 DETAILS ON STUDY VISITS OF INTEREST AND PHONE FOLLOW-UPS

### 1.13.1 V01 - Screening Activities and Run-in Period (2 to 4 weeks prior to randomization)

Screening activities will take place between V01 and V02, which shall be completed between 2 and 4 weeks (up to 28 days) prior to randomization. Randomization will take place on V02. To avoid screen failures, investigators should use their best judgment and only screen subjects they believe will meet all eligibility criteria. Investigator is given this 4-week buffer to allow for (i) review of FAF imaging, (ii) determination of eligibility, (iii) review of clinical lab reports, (iv) determination of initial approximate compliance, among others.

**Screening:** After the ICF has been reviewed, and all questions have been answered, the subject will have the opportunity to decide if they want to participate in the study and sign the ICF. The subject's informed consent must be obtained prior to the performance of any study-related procedures (See section [1.19.3](#) for details).

After obtaining consent, each subject will be assigned a unique screening ID number. This number will be provided by sponsor upon request by investor, unless sponsor informs site that the ID is sequential. The sponsor will inform each site of the subject ID format.

Subjects are then interviewed to determine their preliminary eligibility for enrollment by assessment of inclusion and exclusion criteria. If a subject meets these criteria, all procedures listed in Section [1.2](#) are performed. Investigator is encouraged to send the screened subject's fundus autofluorescence image(s) to

the sponsor or designated reading center as soon as possible to confirm that the subject meets the inclusion criteria.

Subjects' medical history shall be documented according to [1.12.7](#). In addition, historical retinal photographs (including for example FAF, OCT, etc.) shall be collected from subject and included in the subject's binder to help document historical progression of GA. If possible, such files may be received from other sites where subject has previously been seen, after proper authorization has been obtained.

Following screening activities and after receipt and analysis of all clinical laboratory results (excluding PK), all inclusion criteria and all exclusion criteria will be verified, and the subject will be determined as eligible to continue the study or will be withdrawn (screen failure). However, if a subject fails one entry requirement, if some clinical lab values were not properly tested (eg: due to a technical problem), or were inconclusive (eg. if the subject was not fasting or dehydrated at screening), or if retinal photographs or other baseline procedures were of insufficient quality, the investigator may choose to repeat the failed procedure (including re-test of laboratory value) to assess final eligibility.

**Determination of initial approximate compliance during run-in period:** After completion of activities from the first day of screening and if a subject has not yet failed any eligibility criterion, investigator should offer the subject a supply of placebo-containing capsules to assess compliance during the run-in period. Subject should not be informed that the capsules are placebo. Subject should be invited to return for V02, between 2 and 4 weeks after V01. At V02 and preceding randomization, compliance should be assessed and be deemed appropriate if it is greater than approximately 80%. If this is the case, a subject may be randomized and continue the study. If not, PI may decide to further discuss compliance with subject or to withdraw subject from the study.

If there are more eligible subjects than available spots for randomization, the decision about which subject to randomize will be based on practical considerations (distance to clinical site, subject schedule, imaging quality, technical data acquisition, etc.). Non-randomized subjects will be withdrawn from the study as "screen failure."

If a subject is a screen failure but is expected to meet all eligibility criteria in the future, subject may be rescreened upon agreement with the sponsor. Rescreened subjects will re-start the screening phase entirely, which will include receiving a new screening ID number and undergoing the informed consent process again, unless approved otherwise by sponsor.

### 1.13.2 V02 - Randomization Visit (Day 1)

On the day of randomization ("Day 1" or Visit "V02"), eligible subjects selected to participate in the treatment portion of the study are invited to return to the site (unless the medication is directly shipped to them). Subjects receive a "Subject ID" which is used to replace the screening ID. Subject ID will be provided by sponsor or representative, which may be provided orally.

To randomize a subject, investigator is given a sheet containing the list of assignable medication ID (masked), and simply assigns the next available medication ID to the subject (this is possible because blocks and treatment assignment will already have been created at the time of production of the randomization list). The investigator should inform the sponsor in advance so that the site can be properly supplied with study drug. See section [1.9.4](#) for details. An online randomization portal (IWRS) may be used instead of the paper-based randomization code.

The first bottle(s) of study drug can then be dispensed to the subject. Unless sent by email, the study drug is to be dispensed by the investigator or the clinical site pharmacy according to section [1.9.12.3](#).

The day after the first dose, study team should preferably call subjects to check their well-being and remind them to continue taking the study drug at the same time every day, according to section [1.12.11](#).

### **1.13.3 24-hr PK testing authorized upon request by the sponsor**

Because it is unrealistic to perform a long-term pharmacokinetic study in healthy volunteers, detailed pharmacokinetic data of subjects who have been receiving ALK-001 for several months may be more readily acquired by including subjects participating in this study. For that, the investigator, SMC or sponsor might request that some subjects stay at the clinical site for a 24-hour overnight stay. Shorter than 24-hour stays may be admissible and should be agreed upon by the sponsor and the investigator on a case by case basis. Subjects should be informed with reasonable advance notice and should have the choice to accept or refuse to participate, which shall not affect their participation in this study. In case they accept, **the subject will sign a separate informed consent, which shall be IRB-approved**.

For each subject, blood samples should be collected at regular intervals (suggested: 2 and 4 hours post dosing, then every 4 hours for a total of 24 hours post dosing) and processed as described in the bioanalytical manual. In the case of an overnight stay and to reduce the burden on the clinical site, the subject might stay in another designated clinical site (such as a phase 1 unit for example) to perform such pharmacokinetic study.

To avoid unmasking, at least 3 subjects will be asked to participate in this PK sub-study, one in the placebo group, and two in the ALK-001 group.

### **1.13.4 End of treatment period: optional open-label extension period**

Following completion of the initial treatment period of 2 years, subject may be given the choice to enter into a two-year open-label extension study. In order to enroll in this study, the subject will sign a separate informed consent, which shall be IRB-approved. Subjects who elect not to participate in the optional open-label study will be considered to have completed the study.

This optional study will assess the long-term pharmacokinetics of various dose levels of ALK-001, in order to estimate the smallest daily dose level that can maintain approximately 80% of deuterated vitamin A in plasma. In addition, fundus autofluorescence imaging will continue to be acquired and efficacy analyses on the growth rate of geographic atrophy will be performed on all subjects. This study will follow most standard of care practices. **Further details will be provided in future protocol amendments.**

## **1.14 SUBJECT RECRUITMENT, COMPLETION, EARLY DISCONTINUATION, WITHDRAWAL**

### **1.14.1 Subject Recruitment**

Identification: The investigator should use all IRB-permissible means to enroll subjects. The following recruitment channels are suggested:

1. Walk-in visits from new patients
2. Patients referred by colleagues in other locations or practices,

3. Patients referred by the sponsor or representative,
4. Investigator or clinical site's existing patients.

Pre-screen assistance: Sponsor or representatives will be available to assist the investigator in identifying subjects who might meet the eligibility criteria. This assistance may include for example the review of de-identified retinal images or medical charts.

Pre-qualification: Once a prospective subject has been identified, the investigator will reach out to the patient and follow an IRB-approved script to measure the interest of the patient for the study. If a prospective subject expresses an interest in participation, the investigator will review the protocol requirements and eligibility criteria with the subject.

A pre-qualification health questionnaire, typically used for standard practice in the investigator's office may be used by the investigator to pre-qualify subjects who could possibly meet the eligibility criteria. At that time, the investigator should use his/her best judgment so as to initiate screening only for subjects he/she believes would not end up being a screen failure.

Screening: If the prospective subject remains interested and may be eligible, he/she will be invited for the screening visit. Informed consent will be obtained by the investigator.

#### **1.14.2 Subject Completion; Early Discontinuation**

Subjects must remain in the study for the 24-month duration of the treatment period to be considered to have "completed" the study.

Subjects who permanently interrupt treatment before completing the study, or who are withdrawn from the study, will be considered to be "discontinued." Subjects who temporarily interrupt treatment may be invited by the investigator to resume treatment, in which case a protocol deviation shall be noted.

#### **1.14.3 Follow-up After Early Treatment Interruption; Early Termination Visit**

Subjects who temporarily interrupt treatment do not have any special follow-up and may simply continue according to the planned schedule.

Subjects who permanently interrupt treatment will be requested to return the study drug to the site (which may be done by mail), and may be invited to return to the site for an Early Termination visit (ET) (see section 1.2) if a minimum of approximately 1 month has elapsed following the last in-person visit. The ET visit should take place as soon as possible, preferably within 1 month of the permanent treatment interruption. During the ET visit, the following assessments shall be performed in addition to all routine care assessments:

- Physical and ocular examination
- AE
- Concomitant Medications
- Vital signs
- Collection of study drug
- Clinical lab (biochemistry, hematology, lipid, pharmacokinetics, and other optional testing as requested by sponsor)
- ECG: perform if previous ECG is older than ~4 months
- BCVA, LLVA, reading speed: perform if previous testing is older than ~4 months
- Fundus autofluorescence and OCT: perform if previous testing is older than ~4 months

- Microperimetry: perform if previous microperimetry is older than ~4 months
- Fluorescein Angiogram: perform if previous FA is older than ~one year
- Vision questionnaires: perform if previous questionnaires are older than ~6 months

Study team may consult with sponsor to determine if certain activities are required. At the completion of the ET visit, subjects' participation should be discontinued and all study drug returned to the site. There should be no additional follow-up visits.

#### 1.14.4 Temporary or Permanent Interruption of Treatment

Abrupt interruption of treatment is not expected to adversely affect subject health and therefore no special precaution is needed when interrupting treatment. Sponsor shall be informed of any treatment interruption.

- If investigator and sponsor both agree that it is not in the best interest of the subject to continue treatment, for reasons including but not limited to, **non-compliance or health risk**, the subject shall interrupt treatment. Interruption may be temporary if the health risk is expected to resolve in a reasonable time. Subject may be allowed to resume treatment upon mutual decision by investigator and sponsor. In this case, off-treatment duration shall be documented.
- If subject's **treatment assignment is unmasked**, subject shall interrupt treatment, unless decided otherwise by sponsor.
- If a subject's level of **either AST, ALT or Alk Phos is greater than 5 times the upper limit normal (>5x ULN)** for laboratory reference range, subject should interrupt treatment immediately and permanently.
- If a subject's level of **either AST, ALT or Alk Phos is greater than 3 times the upper limit normal (>3x ULN)** for laboratory reference range, subject should be re-tested within 2 weeks. Temporary interruption of treatment is not required until re-test. If subject is unable to be re-tested within 2 weeks, subject should temporarily interrupt treatment until re-test can be performed. If at re-test, the obtained values are lower than 3 times the ULN, the subject can continue or resume treatment. If at re-test the obtained values are still higher than 3 times the ULN, the subject shall interrupt treatment, at least until these levels are measured to be below 3 times the ULN. Once this is the case, subject shall be allowed to resume treatment only upon approval by sponsor.
- Subject shall immediately interrupt treatment if subject is **presumed to have liver injury** according to Hy's law, as indicated by either of the following (assuming no other reason can be found to explain the combination of increase in aminotransferase and bilirubin, including for example alcohol ingestion, congestive heart failure, hepatitis, other drugs, preexisting liver disease, etc.)
  - ALT or AST greater than 3 times the normal upper limit, **with** total bilirubin greater than 2 times normal upper limit **and absent** of other causes of hyperbilirubinemia, **and absent** cholestasis (defined as alkaline phosphatase less than 2 times normal upper limit)
  - ALT or AST greater than 3 times the normal upper limit **with** clinical jaundice
- If during the study, a subject reports **pregnancy**, subject shall immediately and permanently interrupt treatment.
- If a subject's **QTc average value on duplicate ECG is greater than 500 ms or has increased by over 60 ms since the screening visit**, the subject shall temporarily interrupt treatment. Subject may resume treatment only upon approval by PI and sponsor.

If a subject interrupts treatment due to an adverse event, pregnancy or other medical reasons as described above, the subject must be followed at regular intervals until the adverse event normalizes, returns to the subject's baseline condition, or is considered to be related to normal progression of the

patient's condition or unrelated to the study drug. The sponsor and investigator will agree to an acceptable follow-up schedule for these subjects.

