#### **1.14.4 Temporary or Permanent Discontinuation of Treatment**

Abrupt discontinuation of the treatment is not expected to affect subject health risks and therefore no special precaution is needed when discontinuing treatment. Sponsor shall be informed of any discontinuation of treatment.

- If investigator and sponsor both agree that it is not in the best interest of the subject to continue participation, for reasons including but not limited to, **non-compliance or health risk**, the subject shall discontinue treatment. Discontinuation may be temporary if the health risk is expected to resolve in a reasonable time. Subject may be allowed to resume treatment upon mutual decision by investigator and sponsor. In this case, off-treatment duration shall be documented.
- If subject's **treatment assignment is unmasked**, subject shall discontinue treatment, unless decided otherwise by sponsor.

- If one subject's levels of **either AST, ALT or Alk Phos is greater than 5 times the upper limit normal (>5x ULN)** for laboratory reference range, subject should discontinue the treatment immediately and permanently.
- If one subject's levels of **either AST, ALT or Alk Phos is greater than 3 times the upper limit normal (>3x ULN)** for laboratory reference range, subject should be re-tested within 2 weeks. Temporary discontinuation of treatment is not required, and decision shall be at the discretion of the investigator. If the subject is unable to be re-tested within 2 weeks, the subject should permanently discontinue the treatment. If at re-test, the re-tested values are lower than 3 times the ULN, the subject can continue or resume treatment. If at re-test the re-tested values are still higher than 3 times the ULN, the subject shall discontinue treatment, at least until these levels are measured to below 3 times the ULN. Once this is the case, subject shall be allowed to resume treatment only upon approval by sponsor.
- If a subject reports **pregnancy or if a subject's pregnancy test is positive**, subject shall immediately and temporarily discontinue treatment.
- If a subject's **QTc average value on duplicate ECG is greater than 500 ms**, the subject shall temporarily discontinue treatment. Subject may resume treatment only upon approval by sponsor.

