- 17 Genotype and complement may be measured at any time during the study upon sponsor's request. Biological samples required for these tests can be stored at site and shipped in bulk upon request by sponsor.
- 18 ECG should be performed once either at V05, V06 (preferred) or V07 indifferently, per site preference.

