### 1.12.16 12-lead ECG

Vitamin A is not known to affect the ECG. ECG is performed to exclude patients who may have clinically-significant abnormal ECG at baseline, and annually to assess any clinically-meaningful ECG abnormalities. Note that ECGs are frequently interpreted as “abnormal” by the machine internal algorithm even for healthy subjects.

**ECG Recording:** A standard 12-lead resting ECG should preferably be taken supine to the extent feasible. Prior to taking the ECG, the subject shall preferably rest lying down in a quiet setting without distraction (no cell phone, no television) for a few minutes as they are being prepared for the ECG. During ECG recording, subject should not talk or move arms or legs. All recorded ECG traces must be printed out. The same ECG equipment should be used throughout the study if possible. Unscheduled ECGs may be requested by the PI if clinically-indicated.

**Duplicate ECG when necessary:** *If the ECG is interpreted by the machine as abnormal, or if the QTc is greater than 460 ms for male or 480 ms for female*, the person acquiring the ECG should verify all electrode placements and proper attachments, let the subject rest for 5 minutes, and record and print a second ECG trace. Both ECG traces should be printed out then interpreted and reviewed by PI or designated personnel. Special care should be taken during electrode placement, including skin preparation (shave extra hair, gently rub the skin to remove the dead skin layer).

**ECG Interpretation:** The ECG interpreter, who may be the PI or a designated person, should interpret all ECG printout(s) by (a) indicating whether the results are normal or abnormal, (b) providing comments if abnormal, (c) indicating which QTc value to use (otherwise the average of the QTc values will be computed) if more than one ECG trace was done (d) signing or initialing printout(s). The ECG interpreter may provide such information to study team via email, in which case email may replace signature.

**ECG Final Review:** PI is responsible for final review of the ECG by determining whether any abnormalities are clinically significant. PI should complete the following section to document ECG review.

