**Exclusion based on ECG:** To prevent the enrollment of subjects with pre-existing heart conditions detected on ECG, subjects with QTc at screening greater than approximately 460 ms for male and 480 ms for female should not be enrolled in the study unless an approved exception is provided by sponsor.

**Treatment interruption based on ECG:** Treatment may be interrupted or discontinued based on ECG results according to section 1.14.4.

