- Subject permanently interrupts treatment according to one of the reasons of section [1.14.4](#).
- Subject experiences a QTc interval > 500 ms or an increase of QTc greater than 60 ms, based on average QTc value of duplicate ECG, except if approved by sponsor.
- Subject is dead.

- *Lost to follow-up:*

- Subject is lost to follow-up, after every reasonable effort has been made by the study team to contact the subject and determine the reason for discontinuation/withdrawal. All efforts and measures must be documented.

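### The +60 ms QTc interruption rule depends on a duplicate ECG that the protocol does not call for when the trace reads machine-normal and QTc stays at or below 460/480 ms

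*Protocol*

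**What the plan says.** All references are to protocol version 1.1 unless stated.

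- **Interruption rule (1.14.4).** Treatment must be temporarily interrupted if the "QTc average value on duplicate ECG is greater than 500 ms or has increased by over 60 ms since the screening visit". Resumption needs approval by the PI and the sponsor.
- **Withdrawal rule (1.14.6.1).** The same two criteria are reasons for withdrawal unless the sponsor approves otherwise: "Subject experiences a QTc interval > 500 ms or an increase of QTc greater than 60 ms, based on average QTc value of duplicate ECG".
- **When a duplicate is recorded (1.12.16).** The trigger reads "If the ECG is interpreted by the machine as abnormal, or if the QTc is greater than 460 ms for male or 480 ms" for women. The operator then checks the electrodes, rests the subject for five minutes and records a second trace. Rise from screening is not mentioned.
- **Link between the sections.** Section 1.12.16 has no single-trace interruption rule of its own. It says "Treatment may be interrupted or discontinued based on ECG results according to section 1.14.4".
- **Schedule (1.2, footnote 18).** After screening, "ECG should be performed once either at V05, V06 (preferred) or V07 indifferently, per site preference". The next scheduled ECG is at V10 (Month 24), when treatment ends.
- **Protocol version 1.0 (1.14.4).** The criterion was only that the "QTc average value on duplicate ECG is greater than 500 ms". The +60 ms limb came in with version 1.1.

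**The concern.** The subject of both limbs in 1.14.4 is the average on a duplicate ECG, and 1.14.6.1 repeats that condition. If no duplicate is recorded, neither limb can be evaluated. The trigger in 1.12.16 is an absolute QTc threshold or a machine-abnormal reading. That suffices for an absolute criterion of 500 ms but not for a change criterion, because a large rise from a low starting value can end below the threshold.

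The rule was mandatory and numeric so that interruption would not rest on case-by-case judgement. In the uncovered region it falls back on that judgement, and the single mid-study ECG is the only scheduled occasion before Month 24 on which the limb could act.

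**Working it through.** The plan gives no figure to reproduce. The check sets the rule against its trigger.

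**Inputs.** Interruption if the duplicate average exceeds 500 ms, or exceeds screening QTc by more than 60 ms (1.14.4, 1.14.6.1). Duplicate recorded if QTc exceeds 460 ms (men) or 480 ms (women), or if the machine reads abnormal (1.12.16). Screening QTc above about 460/480 ms is excluded (1.8.2, criterion 26).

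**Step 1: the >500 ms limb.** Since 500 > 480 > 460, any first trace above 500 ms exceeds the trigger for either sex. A duplicate is always called for, so there is no gap.

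**Step 2: the +60 ms limb.** Let S be screening QTc and T the on-treatment first-trace QTc. The trace meets the limb if T > S + 60. It escapes the QTc trigger if T ≤ 460 (men) or T ≤ 480 (women). Both can hold only if S + 60 is below the trigger:

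- men: S < 460 − 60 = 400 ms
- women: S < 480 − 60 = 420 ms

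At or above those screening values, any rise over 60 ms passes the trigger and the rule works.

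**Step 3: size of the untriggered rise.** The largest rise that escapes is the trigger minus S.

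| Subject | Screening QTc | Rises that escape the QTc trigger |
|---|---|---|
| Man | 385 ms | >60 to 460 − 385 = 75 ms |
| Man | 370 ms | >60 to 460 − 370 = 90 ms |
| Woman | 400 ms | >60 to 480 − 400 = 80 ms |
| Woman | 390 ms | >60 to 480 − 390 = 90 ms |

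Example: a man going from 385 to 450 ms has risen 65 ms, but 450 ≤ 460. If the machine reads normal, no duplicate is required.

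**Step 4: the machine-reading trigger.** A trace in this region still gets a duplicate if the machine calls it abnormal. Section 1.12.16 says ECGs are often read that way "by the machine internal algorithm even for healthy subjects". This closes part of the gap, by an unknown amount.

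**Step 5: how many subjects could fall in the region.** The documents give no QTc distribution. As an assumption only, take screening QTc as normal with SD 20 ms:

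- men, P(S < 400) = Φ((400 − mean)/20): mean 400 ms, 50%; 410 ms, 31%; 420 ms, 16%
- women, P(S < 420) = Φ((420 − mean)/20): mean 410 ms, 69%; 420 ms, 50%; 430 ms, 31%

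Truncating at the 460/480 ms entry limits changes these by less than 0.5 percentage points. They are shares in whom the gap could arise. Being affected also needs a rise over 60 ms and a machine-normal trace, and neither can be quantified from the documents.

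**Step 6: effect of the fix.** If a rise of more than 60 ms since screening also triggers a duplicate, every first trace with T > S + 60 gets a second trace and the uncovered region is empty.

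**The case against.** The strongest reply is that 1.12.16 does not call its triggers exclusive. A site that sees +65 ms on one trace and knows 1.14.4 could infer that a second trace is needed, and nothing forbids it: the PI may request an unscheduled ECG if clinically indicated, must do the final ECG review, and under 1.5.3 asks the sponsor when sections conflict. Investigator and sponsor can also agree to interrupt for health risk under 1.14.4. SAP 7.5 tabulates QTcF rises over 60 ms with no duplicate condition, so such a rise would be reported.

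None of this makes the limb operate. No step in 1.12.16 tells staff to compare the trace with screening. PI review asks whether abnormalities are clinically significant, and a machine-normal trace at 450 ms may show none. The unscheduled ECG and the health-risk clause are discretionary. The SAP table is reporting and does not protect the individual subject.

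The points on weight do stand. Section 1.12.16 states that vitamin A is not known to affect the ECG. Every subject in the gap has an on-treatment QTc within the protocol's own entry limit. The assumed shares cover only one of three joint conditions, and the number actually affected may be zero. The change also comes late for the main study: SAP 3.1 and 3.2 report 200 subjects randomized and 80% completed.

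**Conclusion.** The concern holds. For men screened below 400 ms and women screened below 420 ms, a rise of more than 60 ms can leave QTc at or below 460/480 ms. If the machine also reads normal, the protocol does not call for the duplicate on which the rule is judged. The cut-offs follow exactly from the protocol's own numbers. The pattern is what results from adding a change criterion in version 1.1 while leaving an absolute trigger that had been adequate for the >500 ms limb alone.

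This should be corrected, but it is not a critical flaw: the >500 ms limb is fully covered, frequent machine-abnormal readings narrow the gap, and the expected harm is small. The shares of 16% to 50% of men and 31% to 69% of women rest wholly on the assumed means and SD. They describe who is exposed to the gap, not who is affected.

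**What to change.** In 1.12.16, add to the conditions for a duplicate ECG: *or if QTc has increased by more than 60 ms since the screening visit*. As a clarification only, add that the average of the duplicate traces, not a value chosen by the reader, is used for 1.14.4 and 1.14.6.1, as those sections already specify.

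The cost is one clause, one sentence and an occasional repeat trace after five minutes' rest, a step already in the protocol. The change cannot help subjects who have completed treatment. It should be carried into the open-label extension, whose details 1.13.4 leaves to future amendments and whose events table (1.3) shows an ECG only at Month 48, and into any later protocol that reuses this text.
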